**10.4. Appendix 4. List of Abbreviations and Definitions**
**10.4.1. Abbreviations**

Abbreviation	Definition
AE	adverse event
AESI	Adverse event of special interest
ALS	amyotrophic lateral sclerosis
ALT	alanine transaminase (SGPT)
ALSAQ-40	Amyotrophic Lateral Sclerosis Assessment Questionnaire
ALSFRS-R	Revised Amyotrophic Lateral Sclerosis Functional Rating Scale
Anti-HCV	hepatitis C antibodies
APB	Abductor pollicis brevis
AST	aspartate transaminase (SGOT)
ATLIS	Accurate Test of Limb Isometric Strength
β-HCG	beta human chorionic gonadotropin
BUN	blood urea nitrogen
cDNA	Complimentary deoxyribose nucleic acid
CDRC	Clinical Data Review Committee
CFR	Code of Federal Regulation
CGIC	Clinical Global Impression of Change
CLI	critical limb ischemia
CONSORT	Consolidated Standards of Reporting Trials
CRA	Clinical Research Associate
CRO	clinical research organization
CS	clinically significant
CTCAE	National Cancer Institute: Common Terminology Criteria for Adverse Events
DMC	Data Monitoring Committee
DNA	deoxyribonucleic acid
DPN	diabetic peripheral neuropathy
DSMB	Data Safety Monitoring Board
EAAT2	excitatory amino acid transporter 2
ECG	electrocardiogram
eCOA	electronic clinical outcome assessment
eCRF	electronic case report form
EDC	electronic data capture system
ePRO	electronic patient reported outcome
ET	early termination from the study
FDA	Food and Drug Administration
FDI	first dorsal interosseus
FVC	forced vital capacity

[figure not shown]
Abbreviation	Definition
GCP	good clinical practices
GGT	gamma-glutamyl transpeptidase
GLP	good laboratory practices
HBV	hepatitis B virus
HBcAb	hepatitis B core antibody (IgG and IgM)
HBsAb	antibody to Hepatitis B surface antigen
HBsAg	hepatitis B surface antigen
HCG	human chorionic gonadotropin
HCV	hepatitis C virus
HCMV	human cytomegalovirus
HDLC-C	High-density lipoprotein cholesterol
HEENT	head, eyes, ears, nose, and throat
HGF	hepatocyte growth factor
HGF-X7	hybrid hepatic growth factor coding sequence expressing two isoforms of HGF, HGF 728 and HGF 723
HHD	Handheld Dynamometer
HIPAA	Health Insurance Portability and Accountability Act
HIV	human immunodeficiency virus
HTLV	human T cell lymphotropic virus
IB	Investigator's Brochure
IBC	Institutional Biosafety Committee
ICF	Informed Consent Form
ID	identifier
IL-6	interleukin 6
IM	intramuscular
IND	Investigational New Drug
INR	International Normalized Ratio
IRB	Institutional Review Board
ISR	Injection site reaction
IV	intravenous
LLOQ	lower limit of quantitation
LMN	lower motor neurons
MCP-1	monocyte chemoattractant protein 1
MRC	Medical Research Council
NCS	not clinically significant
NDA	New Drug Application
NHU	nonhealing foot ulcers
NIH	National Institutes of Health
NMDA	N-methyl-D-aspartate

Abbreviation	Definition
NO	nitrous oxide
NOAEL	No observed adverse event level
NSAID	non-steroidal anti-inflammatory drug
OSP	Office of Science Policy, National Institutes of Health
PAD	peripheral arterial disease
PE	physical examination
PGE2	prostaglandin E2
PGIC	Patient Global Impression of Change
PHI	protected health information
PRO	patient reported outcome
PT	prothrombin time
PTT	partial prothrombin time
QC	quality control
QoL	Quality of Life
RNA	ribonucleic acid
SAE	serious adverse event
SAP	Statistical Analysis Plan
SoA	Schedule of Activities
SOD1	superoxide dismutase 1
SOP	standard operating procedure
SUSAR	suspected unexpected serious adverse reaction
SVC	Slow Vital Capacity
TEAE	treatment-emergent adverse event
TESAE	treatment-emergent serious adverse event
TNF	tumor necrosis factor
UMN	upper motor neuron
VEGF	vascular endothelial growth factor
WFI	water for injection

#### 10.4.2. Definitions

Active Infection	Chronic infection or severe active infection that may compromise the Participant's wellbeing or participation in the study, in the Investigator's judgment
Day 14, etc.	Day 14 (for example) refers specifically to the actual day of the Visit designated as the Day 14 Visit, and not to the 14 th day of the study for a Participant.
End of Study	Completion of the last Visit or procedure shown in the Schedule of Activities for the last Participant remaining in the study

Highly Effective Contraception Method	See Contraceptive Guidance
Injection Site Reaction	An AE located in close proximity to the injection sites on the target muscles and first observed within 48 hr following Study Injections
Investigator	The PI or appropriate study site personnel whom the PI designates to perform a certain duty
Placebo	Placebo comprises 45 mg sodium chloride and 55 mg sucrose in 5 mL water for injection. Engensis vials contain the same excipients.
Safety Analysis Population	All Participants who receive at least one Study Injection
Sponsor	Helixmith Co., Ltd. and its representatives contracted to provide services for study conduct
Study Drug	Engensis or Placebo
Study Injection	Injection of Engensis or Placebo
Participant	Anyone who is consented for Screening
Treatment Arm	The group of Participants assigned to receive Study Drug or the group assigned to receive Placebo during the first 6 months of treatment
Treatment Cycle	Two sets of Study Injections 14 days apart comprising a single dose
VM202	The active pharmaceutical ingredient of Engensis: a novel genomic complementary deoxyribonucleic acid (cDNA) hybrid human hepatocyte growth factor (HGF) coding sequence (HGF-X7) expressing two isoforms of HGF, HGF 728 and HGF 723

## 10.6. Appendix 6. Revised Amyotrophic Lateral Sclerosis Functional Rating Scale

Bulbar	Fine Motor	Gross Motor	Breathing
1. Speech 4. Normal speech processes 3. Detectable speech disturbance 2. Intelligible with repeating 1. Speech combined with nonvocal communication 0. Loss of useful speech	7. Turning in bed 4. Normal 3. Somewhat slow and clumsy, but no help needed 2. Can turn alone or adjust sheets, but with great difficulty 1. Can initiate, but not turn or adjust sheets alone 0. Helpless		
2. Salivation 4. Normal 3. Slight but definite excess of saliva in mouth; may have nighttime drooling 2. Moderately excessive saliva; may have minimal drooling 1. Marked excess of saliva with some drooling 0. Marked drooling; requires constant tissue or handkerchief	8. Walking 4. Normal 3. Early ambulation difficulties 2. Walks with assistance 1. Non-ambulatory functional movement only 0. No purposeful leg movement		
3. Swallowing 4. Normal eating habits 3. Early eating problems-occasional choking 2. Dietary consistency changes 1. Needs supplemental tube feeding 0. NPO (exclusively parenteral or enteral feeding)	9. Climbing stairs 4. Normal 3. Slow 2. Mild unsteadiness or fatigue 1. Needs assistance 0. Cannot do		
4. Handwriting 4. Normal 3. Slow or sloppy; all words are legible 2. Not all words are legible 1. Able to grip pen but unable to write 0. Unable to grip pen	10. Dyspnea 4. None 3. Occurs when walking 2. Occurs with one or more of the following: eating, bathing, dressing (ADL) 1. Occurs at rest, difficulty breathing when either sitting or lying 0. Significant difficulty, considering using mechanical respiratory support		
5a. Cutting Food / Handling Utensils 4. Normal 3. Somewhat slow and clumsy, but no help needed 2. Can cut most foods, although clumsy and slow; some help needed 1. Food must be cut by someone, but can still feed slowly 0. Needs to be fed	11. Orthopnea 4. None 3. Some difficulty sleeping at night due to shortness of breath. Does not routinely use more than two pillows 2. Needs extra pillow in order to sleep (more than two) 1. Can only sleep sitting up 0. Unable to sleep		
5b. Cutting Food / Handling Utensils (Alt. for patients with Gastrostomy) 4. Normal 3. Clumsy but able to perform all manipulations independently 2. Some help needed with closures and fasteners 1. Provides minimal assistance to caregiver 0. Unable to perform any aspect of task	12. Respiratory insufficiency 4. None 3. Intermittent use of BiPAP 2. Continuous use of BiPAP 1. Continuous use of BiPAP during the night and day 0. Invasive mechanical ventilation by intubation or tracheostomy		
6. Dressing and hygiene 4. Normal function 3. Independent and complete self-care with effort or decreased efficiency 2. Intermittent assistance or substitute methods 1. Needs attendant for self-care 0. Total dependence			

---

**10.7. Appendix 7. Amyotrophic Lateral Sclerosis Assessment Questionnaire**

The following is an example of the ALSAQ-40

**Please complete this questionnaire as soon as possible.** If you have any difficulties filling in the questionnaire by yourself, please get someone else to help you with it. However, it is your responses that we are interested in.

The questionnaire consists of a number of statements about difficulties that you may have experienced during the last 2 weeks. There are no right or wrong answers: your first response is likely to be the most accurate for you. Please tick the box which best describes your own experience or feelings.

Please try to answer every question even though some may seem rather similar to others or may not seem relevant to you.

All the information you give will be treated in the strictest confidence.

The following statements all refer to difficulties that you may have had **during the last 2 weeks**.

Please indicate, by ticking the appropriate box, how often the following statements have been true for you.

### Clinical Impression of Change Scale

**1. CGIC - Global Improvement:** Rate total improvement whether or not, in your judgement, it is due entirely to drug treatment. Compared to his/her condition at admission to the project, how much has he/she changed?

[figure not shown]
0 = Not assessed	4 = No change
1 = Very much improved	5 = Minimally worse
2 = Much improved	6 = Much worse
3 = Minimally improved	7 = Very much worse

**2. Efficacy index:** Rate this item on the basis of **drug effect only**.

Select the terms which best describe the degrees of therapeutic effect and side effects and record the number in the box where the two items intersect.

EXAMPLE: Therapeutic effect is rated as 'Moderate' and side effects are judged 'Do not significantly interfere with patient's functioning'.

Therapeutic effect		Side effects			
		None	Does not significantly interfere with patient's functioning	Significantly interferes with patient's functioning	Outweighs therapeutic effect
Marked	Vast improvement. Complete or nearly complete remission of all symptoms	01	02	03	04
Moderate	Decided Improvement. Partial remission of symptoms	05	06	07	08
Minimal	Slight improvement which doesn't alter status of care of patient	09	10	11	12
Unchanged or worse		13	14	15	16
Not assessed = 00					

---

This document is the property of Worldwide Clinical Trials Inc. and may not be duplicated, copied, altered or removed from company without prior approval from Worldwide Quality Assurance or in compliance with Worldwide Standard Operating Procedures.

Worldwide Clinical Trials Controlled Quality Management Document			
 WORLDWIDE CLINICAL TRIALS	Sponsor:	Helixmith Co., Ltd.	
	Protocol Number:	VMALS-002-2	
STATISTICAL ANALYSIS PLAN VERSION 3.0			

LIST OF ABBREVIATIONS

AE	Adverse event
AESI	Adverse event of special interest
ALS	Amyotrophic lateral sclerosis
ALSAQ-40	Amyotrophic Lateral Sclerosis Assessment Questionnaire
ALSFRS-R	Revised Amyotrophic Lateral Sclerosis Functional Rating Scale
ALT	Alanine transaminase (SGPT)
AST	Aspartate transaminase (SGOT)
ATC Level	Anatomic Therapeutic Chemical
ATLIS	Accurate Test of Limb Isometric Strength
BMI	Body Mass Index
BUN	Blood Urea Nitrogen
CGIC	Clinical Global Impression of Change
CK	Creatine Kinase
CM	Centimeter
CS	Clinically significant
CSR	Clinical Study Report
eCRF	Electronic Case Report Form
EDC	Electronic data capture system
GGT	Gamma-glutamyl transpeptidase
HEENT	Head, eyes, ears, nose, and throat
HHD	Handheld Dynamometer
ICF	Informed Consent Form
IM	Intramuscular
ITT	Intent to Treat Population
ISR	Injection site reaction
KG	Kilogram
MedDRA	Medical Dictionary for Regulatory Activities
NCS	Not clinically significant
PGIC	Patient Global Impression of Change
PT	Prothrombin time
PTT	Partial prothrombin time
SAE	Serious adverse event
SAP	Statistical Analysis Plan
SAS	(Statistical Analysis System) statistical software suite developed by SAS Institute

QMD Ref: Worldwide-TMP-ST-005-7.0 Effective: 12Aug2019	Governing QMD: Worldwide-SOP-ST-001
Confidentiality Statement	

This document is the property of Worldwide Clinical Trials Inc. and may not be duplicated, copied, altered or removed from company without prior approval from Worldwide Quality Assurance or in compliance with Worldwide Standard Operating Procedures.

Worldwide Clinical Trials Controlled Quality Management Document			
 WORLDWIDE CLINICAL TRIALS	Sponsor:	Helixmith Co., Ltd.	
	Protocol Number:	VMALS-002-2	
STATISTICAL ANALYSIS PLAN VERSION 3.0			

SOC	System Organ Class
SVC	Slow Vital Capacity
TEAE	Treatment-emergent adverse event
TESAE	Treatment-emergent serious adverse event
WHO	World Health Organization

QMD Ref: Worldwide-TMP-ST-005-7.0 Effective: 12Aug2019	Governing QMD: Worldwide-SOP-ST-001
Confidentiality Statement	

1 INTRODUCTION

This study is a Phase 2a, double-blind, randomized, placebo-controlled, multicenter study designed to assess the safety of intramuscular (IM) administration of Engensis in Participants with Amyotrophic Lateral Sclerosis (ALS) as compared to Placebo. Study Participants will be randomized in a 2:1 ratio to Engensis or Placebo.

This document details the planned statistical analyses for the Helixmith Co., Ltd VMALS-002-2 study titled “A Phase 2a, Double-Blind, Randomized, Placebo-Controlled, Multicenter Study to Assess the Safety of Engensis in Participants with Amyotrophic Lateral Sclerosis”. This document covers all statistical analyses planned in the study.

The proposed analyses are based on the contents of the final protocol, version 3.0 (dated 26-Jan-2021).

2 STUDY OBJECTIVES

Primary objective:

- To evaluate the safety of intramuscular (IM) injections of Engensis in Participants with Amyotrophic Lateral Sclerosis (ALS) compared to Placebo

Exploratory objectives:

- To evaluate changes in muscle function following Engensis injections in ALS Participants compared to Placebo
- To evaluate muscle strength changes following Engensis injections in ALS Participants compared to Placebo
- To evaluate Quality of Life improvement following Engensis injections in ALS Participants compared to Placebo
- To evaluate Patient and Clinical Reported Outcome improvement following Engensis injections in ALS Participants compared to Placebo
- To determine whether IM administration of Engensis has effects on respiratory function in ALS Participants compared to Placebo
- To determine whether IM administration of Engensis has positive effects on survival in ALS Participants compared to Placebo

QMD Ref: Worldwide-TMP-ST-005-7.0 Effective: 12Aug2019	Governing QMD: Worldwide-SOP-ST-001
Confidentiality Statement	

This document is the property of Worldwide Clinical Trials Inc. and may not be duplicated, copied, altered or removed from company without prior approval from Worldwide Quality Assurance or in compliance with Worldwide Standard Operating Procedures.

Worldwide Clinical Trials Controlled Quality Management Document			
 WORLDWIDE CLINICAL TRIALS	Sponsor:	Helixmith Co., Ltd.	
	Protocol Number:	VMALS-002-2	
STATISTICAL ANALYSIS PLAN VERSION 3.0			

- To determine whether IM administration of Engensis has positive effects on muscle atrophy in ALS Participants compared to Placebo

3 ENDPOINTS

3.1 Primary Endpoint

- Incidence of treatment-emergent adverse events (TEAEs) and treatment-emergent serious adverse events (TESAEs) for Engensis compared to Placebo
- Incidence of injection site reactions for Engensis compared to Placebo
- Incidence of clinically significant laboratory values for Engensis compared to Placebo

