#### Rationale:

The purpose of this study is to evaluate the safety of intramuscular (IM) administration of Engensis in Participants with Amyotrophic Lateral Sclerosis (ALS) as compared to Placebo. Safety will be assessed by incidences of treatment-emergent adverse events (TEAEs), treatment-emergent serious adverse events (TESAEs), injection site reactions (ISRs) and other adverse events of special interest (AESIs), and the clinically significant laboratory values after injections for Engensis compared to Placebo. Exploratory endpoints include assessment of muscle function using the Revised Amyotrophic Lateral Sclerosis Functional Rating Scale (ALSFRS-R) and ALSFRS-R subscores for Fine and Gross Motor Function; muscle strength by quantitative testing using Handheld Dynamometry (HHD) and the Accurate Test of Limb Isometric Strength (ATLIS) where available; quality of life using the ALS Assessment Questionnaire (ALSAQ-40); patient global impression of change (PGIC), and clinical global impression of change (CGIC); and evaluation of lung function using Slow Vital Capacity (SVC). Muscle biopsies will be performed during the study for future biomarker analyses.

Engensis contains the active pharmaceutical ingredient VM202, a novel genomic complementary deoxyribonucleic acid (cDNA) hybrid human hepatocyte growth factor (HGF) coding sequence (HGF-X7) expressing two isoforms of HGF, HGF728 and HGF723, being developed for treatment of ALS.

Data from Helixmith's first clinical trial in ALS, the Phase 1/2 ALS study (VMALS-001), which included 18 Participants who were followed for 9 months, suggested that targeted delivery of HGF to motor neurons via intramuscular (IM) injections of Engensis was safe and well-tolerated. Safety assessments during the study included reports of 79 adverse events (AEs) in 17 Participants (94.4%), including 26 mild injection site reactions (Grade 1). Five SAEs were reported in 3 Participants. Only injection site reactions were considered related to study treatment. Following injections until Day 90, a plateau or a relative slowing in decline of the ALSFRS-R scores and muscle strength was noted, suggesting a slowing of disease progression. After 90 days, the plateau was no longer observed in the ALSFRS-R, with the notable exception of a trend toward better preservation of bulbar and breathing functions as measured by the ALSFRS-R.

---

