### **5.3. Number of Participants**

The target sample size is 18 Participants who will be randomized in a 2:1 ratio to Engensis or Placebo (12:6).

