### **8.5.4. Adverse Events of Special Interest**

#### **Categories of AESIs**

There are three main categories of AESIs as presented below: 1) those considered to be related to the angiogenesis potential of Engensis, 2) other medical problems in this patient population, and 3) injection site reactions.

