### 9.1. Sample Size Determination

A sample size of 18 Participants was chosen for safety assessments and preliminary evaluation of exploratory endpoints.

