**Table 6: Injection Site Reaction Grading**

Reaction at Injection Site a	Mild (Grade 1)	Moderate (Grade 2)	Severe (Grade 3)	Potentially Life-Threatening (Grade 4)
Pain, tenderness	Mild discomfort to touch, with or without warmth, erythema, itching	Symptoms with or without swelling and/or phlebitis	Symptoms with or without swelling or phlebitis or mild infection	Symptoms with severe infection or tissue injury or ulceration
	Does not interfere with daily activity	Interferes with daily activity	Precludes daily activity	Requires advanced medical and/or surgical care, including intravenous (IV) medications
	No or local treatment	Use of non-narcotic pain reliever	Use of narcotic pain reliever and/or oral antibiotics	
Erythema, itching, urticaria	Mild, localized itching, erythema or urticaria	Symptoms with skin changes beyond local injection site(s)	Symptoms with widespread skin changes	Bronchospasm, anaphylactoid, or anaphylactic reaction
	Does not interfere with activity	Interferes with movement and daily activity	Interferes with daily activity	Requires advanced medical care, including IV medication
	Use of topical treatment	Use of NSAIDs and/or antihistamines	Use of oral steroids or immuno-suppressives	
Bruising, swelling, bleeding	Mild, localized swelling, ecchymosis or hematoma	Moderate ecchymosis or hematoma	Extensive ecchymoses, large hematoma	Hypotension, life-threatening consequences
	Does not interfere with activity	Interferes with daily activity	Precludes activity	Requires transfusion, urgent intervention
	No treatment	Requires leg elevation, conservative treatment	Requires minimally invasive drainage	

Abbreviations: NSAID = non-steroidal anti-inflammatory drugs

a Injection site reactions are a category of AESIs and should be recorded as AEs using these grading guidelines.

---

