- This definition is not intended to include experiences of relatively minor medical significance such as uncomplicated headache, nausea, vomiting, diarrhea, influenza, and accidental trauma (e.g., sprained ankle), which may interfere with or prevent everyday life functions but do not constitute a substantial disruption.

QMD Ref: Worldwide-TMP-ST-005-7.0 Effective: 12Aug2019	Governing QMD: Worldwide-SOP-ST-001
Confidentiality Statement	

This document is the property of Worldwide Clinical Trials Inc. and may not be duplicated, copied, altered or removed from company without prior approval from Worldwide Quality Assurance or in compliance with Worldwide Standard Operating Procedures.

Worldwide Clinical Trials Controlled Quality Management Document			
 WORLDWIDE CLINICAL TRIALS	Sponsor:	Helixmith Co., Ltd.	
Protocol Number:			VMALS-002-2
STATISTICAL ANALYSIS PLAN VERSION 3.0			

- e Is a congenital anomaly/birth defect
- f Other situations:
 - Medical or scientific judgment should be exercised in deciding whether SAE reporting is appropriate in other situations such as important medical events that may not be immediately life-threatening or result in death or hospitalization but may jeopardize the Participant or may require medical or surgical intervention to prevent one of the other outcomes listed in the above definition. These events should usually be considered serious.
 - Examples of such events include invasive or malignant cancers; intensive treatment in an emergency room or at home for allergic bronchospasm, blood dyscrasias, or convulsions that do not result in hospitalization; or development of drug dependency or drug abuse.

Treatment-Emergent Serious Adverse Event (TESAE)

- A serious event that emerges during treatment, having been absent at pretreatment, or worsens relative to the pretreatment state, as defined in the EP Guidance.
- The TESAE is not related to causality / drug relatedness. It may or may not be related to the drug but is considered a TESAE due to its appearance at or after the treatment has been administered.

Adverse Events of Special Interests (AESI)

There are 4 main categories of AESIs that will be considered in the study:

1. Related to the angiogenesis potential of Engensis
 - Atherosclerosis
 - Cancer
2. Other medical problems in this patient population
 - Pulmonary Medical Problems
 - Progressive Muscle Weakness
 - Bulbar Disease
3. Injection site reactions
4. COVID-19 infections

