The following tables will be presented:

- Summary of TEAE (Table 14.3.1.1)

QMD Ref: Worldwide-TMP-ST-005-7.0 Effective: 12Aug2019	Governing QMD: Worldwide-SOP-ST-001
Confidentiality Statement	

This document is the property of Worldwide Clinical Trials Inc. and may not be duplicated, copied, altered or removed from company without prior approval from Worldwide Quality Assurance or in compliance with Worldwide Standard Operating Procedures.

Worldwide Clinical Trials Controlled Quality Management Document			
 WORLDWIDE CLINICAL TRIALS	Sponsor:	Helixmith Co., Ltd.	
	Protocol Number:	VMALS-002-2	
STATISTICAL ANALYSIS PLAN VERSION 3.0			

- TEAEs organized by SOC and PT (Table 14.3.1.2)
- TESAEs organized by SOC and PT (Table 14.3.1.3)
- TEAEs organized by SOC and PT and Maximum Severity (Table 14.3.1.4)
- TEAEs organized by SOC and PT and Maximum Relationship (Table 14.3.1.5)
- TESAEs organized by SOC and PT and Maximum Severity (Table 14.3.1.6)
- TESAEs organized by SOC and PT and Maximum Relationship (Table 14.3.1.7)
- Incidence Injection site reactions by SOC and PT (Table 14.3.1.8)
- Incidence of clinically significant laboratory values (Table 14.3.1.9)
- AESIs organized by SOC and (Table 14.3.1.10)
- TEAEs leading to study discontinuation by SOC and PT (Table 14.3.1.11)
- TESAEs leading to study discontinuation by SOC and PT (Table 14.3.1.12)
- TEAEs leading to study drug withdrawal by SOC and PT (Table 14.3.1.13)
- TESAEs leading to study drug withdrawal by SOC and PT (Table 14.3.1.14)
- TEAEs related to study medication by SOC and PT (Table 14.3.1.15)
- TESAEs related to study medication by SOC and PT (Table 14.3.1.16)

The following listings will be provided:

- All AEs (Listing 16.2.7.1)
- AESIs (Listing 16.2.7.2)
- TESAEs (Listing 16.2.7.3)
- Injection Site Reactions (Listing 16.2.7.4)
- TEAEs leading to study discontinuation (Listing 16.2.7.5)
- TEAEs related to study medication (Listing 16.2.7.6)
- TESAEs leading to death (Listing 16.2.7.7)

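### Injection site reactions are counted again in the any-TEAE, related-TEAE and AESI totals, and no listed table shows these totals without them

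*SAP*

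**What the plan says.** SAP Section 3.1 lists three primary safety endpoints: "Incidence of treatment-emergent adverse events (TEAEs) and treatment-emergent serious adverse events (TESAEs) for Engensis compared to Placebo", the incidence of ISRs, and the incidence of clinically significant laboratory values. Protocol Section 9.3.1 makes the safety analysis descriptive, without formal testing.

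ISRs are not kept apart from the first endpoint. The footnote to Protocol Table 6 states: "Injection site reactions are a category of AESIs and should be recorded as AEs using these grading guidelines". Footnote 24 of the Schedule of Activities likewise has the worst reaction recorded as a TEAE and treated as an AESI.

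SAP Section 6.14.1 plans an overall TEAE summary (Table 14.3.1.1), TEAEs by SOC and PT (14.3.1.2), ISRs (14.3.1.8), AESIs (14.3.1.10) and TEAEs related to study medication (14.3.1.15). No title in that list, or in SAP Section 11, describes a version without ISRs. An event with a missing relationship is counted as related. On the earlier ALS study, the protocol synopsis says: "Only injection site reactions were considered related to study treatment".

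The two documents also differ on what an AESI is. SAP Section 6.14.1 says "There are 4 main categories of AESIs that will be considered in the study", the fourth being COVID-19 infection. Protocol Section 8.5.4 says "There are three main categories of AESIs as presented below", and COVID-19 is not among them. SAP Section 9 declares no changes to the protocol's analysis.

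**The concern.** Placebo participants receive the same number of injections at the same sites as Engensis participants, so the needle alone can produce ISRs in both arms. A participant with one mild ISR already counts as having a TEAE and an AESI. If the investigator judges the reaction related, which a blinded investigator may do in either arm, the participant also counts as having a related TEAE. The more common ISRs are, the closer these totals come to 100% in both arms, and the less room they leave for a difference in other events to show.

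SOC and PT rows do not add up to the missing quantity. One participant can appear in several rows, so the share with any non-ISR event, or any non-ISR related event, cannot be read from them. An ISR-free row chosen after unblinding would be post hoc.

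The AESI table has a further problem that does not depend on the ISR rate. Its title gives only SOC and PT, so cancer and atherosclerosis, the angiogenesis-related concerns, share one total with ISRs and with the pulmonary, weakness and bulbar events expected in ALS.

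**Working it through.** **Injection counts.** From Protocol Tables 1 to 3, one side receives 2+2+8+8+2+2+2+20+12+6 = 64 injections. Both sides give 128 per visit, two visits give 256 per cycle, and three cycles give 768. This matches Protocol Section 4.4.2. The earlier ALS study gave 256 injections over four visits, one third of 768.

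**Participant-level ISR rate, q.** The synopsis reports 79 AEs in 17 of 18 participants (94.4%), of which 26 were ISRs, all mild. It does not say how many participants had an ISR.
- If at most one ISR was recorded per visit, at least 26/4 = 6.5, so 7 participants, had one. At most 17 did. The range is 39% to 94%.
- If counts follow a Poisson distribution with mean 26/18 = 1.44, the share is 1 − exp(−1.44) = 76%.
- At the same rate per visit (26/72 = 0.361) over six visits, the share is 1 − exp(−2.17) = 88.5%. Scaled instead to three times the injections, it is 1 − exp(−4.33) = 98.7%.
- In the other direction, the clinical-experience text just before Protocol Section 2.2.6.1 gives injection-site pain in 1–4% of participants, similar to placebo. If that figure applied to each visit, six visits would give 1 − 0.99^6 = 5.9% to 1 − 0.96^6 = 21.7%.

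**Effect on a total.** Let p be the rate of any non-ISR event. Assume that q is equal in both arms and independent of other events. Then

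rate of any event = q + (1 − q)p, and visible difference = (1 − q) × (p in Engensis − p in Placebo).

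| Assumption for q | q | Share of a true non-ISR difference still visible |
|---|---|---|
| 1–4% per participant | 1–4% | 0.99–0.96 |
| 4% per visit, six visits | 21.7% | 0.78 |
| Earlier study, lower limit above | 39% | 0.61 |
| Earlier study, Poisson, four visits | 76% | 0.24 |
| Same rate per visit, six visits | 88.5% | 0.12 |
| Scaled to injections | 98.7% | 0.01 |

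**What remains once ISRs are removed.** The earlier study had 79 − 26 = 53 non-ISR AEs, or 53/18 = 2.94 per participant over nine months. A Poisson spread gives 1 − exp(−2.94) = 95% with at least one. Taking nine months as 270 days, 180 days gives 2.94 × 180/270 = 1.96 per participant, and 1 − exp(−1.96) = 86%. Clustering of events would lower both figures. That study was open label with everyone treated. If 86% were nevertheless the placebo rate here, the largest possible Engensis excess in any non-ISR TEAE would be 14 points, less than one placebo participant (1/6 = 16.7 points).

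**Related TEAEs.** The non-ISR related count in the earlier study was zero among 18 participants. On that pattern the total in Table 14.3.1.15 would consist only of ISRs and so would overlap the ISR endpoint, while an ISR-excluded row would start near zero and any event would be visible.

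**ISR window.** Schedule of Activities footnote 24 has the participant asked about reactions within 2 to 3 days. Protocol Sections 8.5.4.3 and 10.4.2 require an ISR to be first observed within 48 hours. A reaction first reported on day 3 could therefore be a TEAE under footnote 24 and fail the ISR definition, and so would fall on the non-ISR side of any split.

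**The case against.** The strongest reply is that ISRs are not what limits the any-TEAE total. On the earlier study's figures nearly everyone with ALS has some other adverse event, so removing ISRs may still leave a row close to its ceiling. This stands, and it makes the ISR-excluded any-TEAE row useful but not decisive. The same applies to AESIs, where disease progression alone can fill the total.

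It is also fair that the ISR rate is not known, that the only participant-level figure in the documents (1–4%) would cause almost no masking, and that the 94.4% is any AE, not ISRs. The 1–4% may not transfer, however. The Phase 3 neuropathy regimen in Protocol Section 4.4.2 was 8 mg per visit at 0.25 mg per injection, or 32 injections, against 128 here.

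Non-ISR events do not disappear from the report. SOC and PT rows, separate TESAE tables, severity tables and full listings all remain, and with 18 participants a count can be made by hand from Listings 16.2.7.1 and 16.2.7.4. The SAP gives table titles only. The shells are not shown, so an ISR-excluded row or an AESI grouping may already exist. SAP Section 6 also allows additional tables. These points limit the consequence, but they do not put a prespecified row into the plan.

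A reader might infer that the TEAE comparison will saturate and tell us nothing about Engensis. The documents do not support that. No source fixes q, mild ISRs would be unlikely to fill the TESAE part of the endpoint, and the detailed rows stay informative.

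**Conclusion.** The overlap is documented and worth correcting, but its effect cannot be sized from the documents. Depending on q, between about 99% and about 1% of a true non-ISR difference would show in a total. This assumes equal ISR rates in the two arms and independence from other events, and the upper values of q also rest on a Poisson spread. The related-TEAE total has the most to gain, because nothing but ISRs was judged related before. The any-TEAE total has less to gain, because it may be near its ceiling either way.

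A reader might also infer that the ISR-excluded row should replace the protocol's TEAE endpoint as the main comparison. That does not follow. It would change how a protocol primary endpoint is read, and the row itself may be close to its ceiling. Nor would the split supply power. Of the sample size, the protocol says only: "A sample size of 18 Participants was chosen for safety assessments and preliminary evaluation of exploratory endpoints". With 12 against 6, the gain is visibility of events.

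The COVID-19 mismatch between SAP Section 6.14.1 and Protocol Section 8.5.4 is a definite inconsistency whatever the ISR rate. Overall this is a cheap improvement to make before database lock.

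**What to change.** In SAP Section 6.14.1:
- Add prespecified supplementary rows excluding ISRs (participants, percentage, number of events) to Tables 14.3.1.1 and 14.3.1.15, beside the existing totals. Keep the protocol's TEAE endpoint and Table 14.3.1.8 as they are.
- Present Table 14.3.1.10 by AESI category, then by SOC and PT.
- Reconcile the COVID-19 category with Protocol Section 8.5.4. If it is kept, record it in SAP Section 9.

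Reconcile the 2-to-3-day contact in Schedule of Activities footnote 24 with the 48-hour rule in Protocol Sections 8.5.4.3 and 10.4.2, and state how a reaction first reported after 48 hours is classified. Without this, the ISR-excluded rows are ambiguous.

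The cost is SAP wording, clarification of the protocol passages concerned and slightly longer tables. No new data are needed.
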